There is further evidence that patients undergoing vaginoplasty surgery may have preoperative pelvic floor dysfunction symptoms that should be addressed before and after surgery. In a retrospective study by Manrique et al (5), patients scheduled to undergo male-to-female vaginoplasty were evaluated by a physical therapist for pelvic floor dysfunction and patients with pelvic floor symptoms underwent pre- and postoperative PFPT. The authors found that of the 40 patients evaluated, 31 (77.5%) were found to be symptomatic and that physical therapy significantly reduced severity of symptoms and its impact on daily living following surgery.

Currently, perioperative PFPT is not standard of care for all patients who undergo vaginoplasty surgery. While some practices have implemented these new programs, and the above data exist on outcomes associated with perioperative PFPT in transgender women undergoing vaginoplasty, no study has compared implementation of perioperative PFPT to routine care (no perioperative PFPT). Therefore, the primary objective of this study to compare the effectiveness of postoperative PFPT compared to no PFPT in transgender women undergoing vaginoplasty surgery for gender affirmation. Secondary objectives of the study are 1) to describe the incidence of preoperative pelvic floor dysfunction in transgender women undergoing PFPT and 2) to compare the

effectiveness of postoperative PFPT alone to pre- and postoperative PFPT in these patients.

STUDY METHODS

Study Design: Randomized double-blind study

Both subjects and the surgeon performing the surgery as well as the personnel administering questionnaires to patients postoperatively will be blind to randomization

Primary Aim

To compare the effectiveness of postoperative PFPT compared to no PFPT in transgender women undergoing vaginoplasty.

Primary Outcome: Patient reported ease of dilation at 12 weeks (VAS 0-10)

Secondary Outcome: Severity of pelvic floor dysfunction at 12 weeks (questionnaires)

Secondary Aims

To describe the incidence of preoperative pelvic floor dysfunction in transgender women undergoing PFPT.

To compare the effectiveness of postoperative PFPT alone to pre- and postoperative PFPT in these patients.

Primary Outcome: Patient reported ease of dilation at 12 weeks (VAS 0-10)

Secondary Outcome: Severity of pelvic floor dysfunction at 12 weeks (questionnaires)

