- Subjective assessment of bowel and bladder function
- Visual and external palpation and assessment of external pelvic floor region
- Intravaginal pelvic floor assessment
- Pelvic floor muscle dynamics and coordination assessment
- Instruction of pelvic floor coordination and lengthening
- Discussion of dilator program and progression
- Home program with instructions

6 weeks:

- External scar assessment and treatment if tissue healing allows
- Instruction to patient of scar mobilizations
- Intravaginal pelvic floor assessment and treatment if indicated
- Review of pelvic floor lengthening and coordination
- Review and progression of dilator program if appropriate
- Assessment of current bowel/bladder symptoms; home program and instructions to address these symptoms

3) Preoperative PFPT and Postoperative PFPT

Patients will present to see the physical therapist 3 weeks before surgery, 3 weeks and 6 weeks postoperatively. The following interventions will be performed:

Preoperative:

- Diaphragmatic breathing
- Discuss dilator positioning/introduce dilator program
- External pelvic floor assessment
- Teach pelvic floor coordination
- Assessment of current bowel/bladder symptoms; home program and instructions to address these symptoms

3 weeks:

- Subjective assessment of bowel and bladder function
- Visual and external palpation and assessment of external pelvic floor region
- Intravaginal pelvic floor assessment
- Pelvic floor muscle dynamics and coordination assessment
- Instruction of pelvic floor coordination and lengthening
- Discussion of dilator program and progression
- Home program with instructions

6 weeks:

- External scar assessment and treatment if tissue healing allows
- Instruction to patient of scar mobilizations
- Intravaginal pelvic floor assessment and treatment if indicated
- Review of pelvic floor lengthening and coordination
- Review and progression of dilator program if appropriate
- Assessment of current bowel/bladder symptoms; home program and instructions to address these symptoms

Study Questionnaires & Exams

All patients will be administered questionnaires preoperatively and 12 weeks postoperatively. The following questionnaires will be administered:

Preoperatively:

- CRAD-8 and UDI-6
- PFIQ-7

Postoperatively 1 week (at the time of routine dilation teaching):

- Vaginal length (routine exam)

Postoperatively 12 weeks:

- CRAD-8 and UDI-6
- PFIQ-7
- PGI-I
- Ease of Passing Dilator (VAS 0-10)
- Pain with Dilation (VAS 0-10)

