de-identified data export mechanism to common statistical packages. The system was developed by a multi-institutional consortium which was initiated at Vanderbilt University and includes the Cleveland Clinic. The database is hosted at the Cleveland Clinic Research Datacenter in the JCN basement and is managed by the Quantitative Health Sciences Department. The system is protected by a login and Secure Sockets Layers (SSL) encryption. Data collection is customized for each study as based on a study-specific data dictionary defined by the research team with guidance from the REDCap administrator in Quantitative Health Sciences at the Cleveland Clinic.

POWER ANALYSIS & STATISTICS

There will be 2 arms to this study: No Postoperative PFPT and Postoperative PFPT. The Postoperative PFPT arm will be further randomized into two other arms: Postoperative PFPT Only and Preoperative and Postoperative PFPT.

The primary aim is to compare the effectiveness of postoperative PFPT compared to no PFPT in transgender women undergoing vaginoplasty using Ease of Dilation (VAS 0-10) as the primary outcome. We determined that 17 subjects in each arm were needed to detect a difference of 2 (+/-1) points between the two groups (No Postoperative PFPT vs Postoperative PFPT) with 80% power and a significance level of 0.05. We will account for potential subject drop out and loss to follow-up as well as unforeseen factors in recruiting and will plan to recruit 20 subjects to each arm, for a total of 40 subjects.

Continuous descriptive data will be reported as mean and standard deviation (\pm SD) or median with interquartile range (IQR), depending on distribution. Categorical data will be reported as frequencies, using percentages. Ease of dilation and pelvic floor symptoms will be compared between arms (No PFPT vs Postoperative PFPT). The investigators also plan to perform a subgroup analyses, comparing patients who

underwent postoperative PFPT only to those who underwent both preoperative and postoperative PFPT.

Ease of dilation (mean) and pelvic floor symptoms (mean difference from baseline) will be compared as a continuous variables using a student' t test to compare between the two groups. Binary logistic regression will be used to assess the influence of various patient factors on the patient reported ease of dilation as well as pelvic floor symptoms and results will be reported as odds ratios with 95% confidence intervals.

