JMP 14.0 (SAS Institute Inc., Cary, NC) will be used for all statistical analyses. The primary investigator ([name]) will perform the statistical analysis. All results yielding $p < 0.05$ will be deemed statistically significant.

All analyses will be conducted using an intention-to-treat principle. The investigators anticipate that some non-adherence to the assigned intervention (e.g. crossover to the postoperative PFPT arm) may occur if patients are determined to be symptomatic requiring PFPT per the surgeon's discretion, and as these protocol deviations will bias the results towards superiority of the intervention, a per-protocol sensitivity analysis has also been planned.

REFERENCES

- 4) Jiang DD¹, Gallagher S, Burchill L, Berli J, Dugi D. Implementation of a Pelvic Floor Physical Therapy Program for Transgender Women Undergoing Gender-Affirming Vaginoplasty. *Obstet Gynecol* 2019; 133(5):1003-1011.

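### The primary ease-of-dilation comparison is a valid unadjusted t test, but it makes no use of the pelvic floor scores planned before surgery and may give up some precision in a 20 v 20 trial

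*Combined protocol and SAP*

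**What the plan says.** Under Study Methods the primary endpoint is given as "Primary Outcome: Patient reported ease of dilation at 12 weeks (VAS 0-10"). Under Power Analysis & Statistics the comparison is described as follows: "Ease of dilation (mean) and pelvic floor symptoms (mean difference from baseline) will be compared as a continuous variables using a student' t test". Symptom scores therefore use their own baseline through a change score. Ease of dilation is compared on its 12-week mean alone.

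Under Study Questionnaires & Exams: "All patients will be administered questionnaires preoperatively and 12 weeks postoperatively". The preoperative list is CRAD-8, UDI-6 and PFIQ-7. Ease of passing the dilator appears only in the 12-week list, so the primary outcome has no baseline value.

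The analysis section also plans a binary logistic regression "to assess the influence of various patient factors on the patient reported ease of dilation". It names no factors, cut-point or treatment term.

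The section on recruitment, enrollment and randomization describes no stratification or minimisation and places randomisation after consent. One sub-arm has a physical therapy visit 3 weeks before surgery. The preoperative questionnaires are not timed against randomisation or against that visit.

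**The concern.** With about 20 patients per arm, noticeable chance differences in baseline pelvic floor status are quite possible. The Background cites preoperative pelvic floor dysfunction in 42% of one series and symptoms in 77.5% of another, so patients are likely to enter with varied status. If that status is related to how easily patients dilate at 12 weeks, part of the outcome variance could be explained by a score the trial already plans to collect, and the arm difference could be corrected for whatever imbalance occurs.

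The planned logistic regression does not do this. It would need the VAS split in two, and it yields odds ratios for patient factors, not an adjusted mean difference between arms. Without a prespecified adjusted analysis, any imbalance that appears would have to be handled post hoc.

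At stake are some power and interval width, and how convincing the result looks if the arms differ at baseline.

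**Working it through.** **Inputs from the document.** Sample size: "17 subjects in each arm were needed to detect a difference of 2 (+/-1) points between the two groups", "with 80% power and a significance level of 0.05". Recruitment: "will plan to recruit 20 subjects to each arm, for a total of 40 subjects". Sidedness is not stated; two-sided is assumed.

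**Inputs assumed.** SD of the VAS, and the correlation R between a preoperative score and 12-week ease of dilation. Neither is given.

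**Step 1: reproduce 17 per arm.** Normal approximation: n = 2(1.960 + 0.842)² × (SD/difference)².
- Difference 2, SD 1: n = 3.9, so 4 per arm; the t-based calculation gives 5.09, so 6. The figure of 17 is not reproduced.
- Difference 2, SD 2: n = 15.7, so 16; the t-based calculation gives 16.7, so 17. Reproduced.

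So 17 corresponds to a standardised difference of 1.0, and SD 2 is used below. Going from 17 to 20 allows for 15% loss (17/0.85 = 20).

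**Step 2: the planned test at 20 per arm.** SE = 2 × √(2/20) = 0.63. The 95% CI half-width is 1.28 on 38 df. Noncentral-t power for 2 points is 86.9%.

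**Step 3: one covariate.** Variance relative to the t test = (1 − R²) × (1 + 1/(N − 4)), with N = 40 and N − 3 = 37 error df.

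| R | Relative variance | CI half-width | Power |
|---|---|---|---|
| unadjusted | 1 | 1.28 | 86.9% |
| 0 | 1.028 | 1.30 | 85.9% |
| 0.3 | 0.935 | 1.24 | 89.0% |
| 0.5 | 0.771 | 1.13 | 93.9% |

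Break-even is where (1 − R²)(37/36) = 1, that is R = √(1/37) = 0.16. Simulation with 10,000 runs per setting gave adjusted power of 86.1%, 88.9% and 94.0% (0.9395) at R = 0, 0.3 and 0.5, in agreement.

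At 17 per arm, power is 80.7% unadjusted and 79.3%, 83.0% and 89.4% at the same three correlations; break-even is 0.18. The worst-case cost is therefore 86.9 − 85.9 = 1.0 point at 20 per arm and 80.7 − 79.3 = 1.4 points at 17.

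**Step 4: all three scores.** At 20 per arm, break-even rises to a multiple correlation of 0.28, and power falls to 83.8% if the scores are unrelated to the outcome. One covariate is the safer choice.

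**Step 5: chance imbalance at 20 per arm.** The arm difference in a standardised baseline score has SD √(2/20) = 0.32; the chance of a gap above 0.5 SD is about 11%. A one-SE imbalance shifts the unadjusted difference by R × 2 × 0.316: 0.06 points at R = 0.1, 0.19 at 0.3 and 0.32 at 0.5, against an SE of 0.63.

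**Step 6: the other reading of ±1.** If it is the SD, power at 17 per arm is already above 99.9%. The relative variances in Step 3 do not depend on the SD, so the interval would still narrow in proportion, but power would hardly change.

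**The case against.** The strongest reply is that nothing is wrong with the planned test. Over randomisation it is unbiased, and its standard error already allows for chance imbalance. Simulated type I error was 4.6% to 5.1%. That stands. A reader might infer from the missing adjustment that the primary result would be biased or its p-value unreliable; the documents do not support that. This is a point about efficiency.

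A reader might also infer that the plan certainly loses precision. That does not follow either. The scores measure pelvic floor dysfunction, while the outcome concerns a canal created at surgery. The documents give no correlation, and below about 0.16 adjustment costs a little precision. Nor does the planned regression show that the sponsor expects these scores to predict ease of dilation: its factors are unnamed and need not include them.

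The imbalance shift should be read against the standard error. The 0.32 points is the top of the assumed range and half of one SE (0.32/0.63).

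Finally, adjustment is not automatically safe here. If the questionnaires were completed after the preoperative therapy visit, scores in that sub-arm could reflect treatment, and adjusting for them could bias a comparison that is now unbiased. This objection stands in full and shapes the fix.

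What survives is the asymmetry: a small, bounded loss against a gain of about 2 to 9 power points (2.1 and 7.0 at 20 per arm, 2.3 and 8.7 at 17) if the correlation is 0.3 to 0.5.

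**Conclusion.** The point holds as a cheap improvement of minor priority. The primary analysis is sound but makes no use of baseline data planned for every patient, and no other planned analysis supplies an adjusted mean difference. The likely benefit runs from slightly negative to a useful gain in precision: a variance change of +2.8% to −23% over correlations of 0 to 0.5 at 20 per arm.

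This rests on the assumed correlation range and, for the power figures, on SD 2, which is back-solved from 17 per arm. The undefined ±1 is a separate and larger matter. Until it is settled, the power gain cannot be fixed more closely.

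**What to change.** 1. State that the preoperative questionnaires are completed after consent and before randomisation, and so before any preoperative therapy visit.
2. Prespecify as primary a linear model of 12-week ease of dilation on randomised group plus one such score, named in advance (for example PFIQ-7; the documents give no ground for preferring one score).
3. Report the adjusted mean difference in VAS points with its 95% CI.
4. Keep the unadjusted t test as a sensitivity analysis.

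The cost is plan wording, a fixed questionnaire time and one error degree of freedom, worth about 1.0 to 1.4 power points if the score is unrelated to the outcome. No new instrument is needed. A score taken after randomisation should not be used as the covariate.

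### The patient-factor analysis assigns binary logistic regression to outcomes the plan treats as continuous, with no cut defined; name linear regression in advance instead.

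*Combined protocol and SAP*

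**What the plan says.** All references are to the combined protocol and SAP.

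- STUDY METHODS, Primary Aim, defines the two outcomes: "Primary Outcome: Patient reported ease of dilation at 12 weeks (VAS 0-10") and "Secondary Outcome: Severity of pelvic floor dysfunction at 12 weeks (questionnaires"). The first is a score and the second is a severity. Neither is defined as present or absent.
- Study Questionnaires & Exams lists the 12-week instruments, including "Ease of Passing Dilator (VAS 0-10"), with no threshold for any of them.
- POWER ANALYSIS & STATISTICS, on the main comparison: "Ease of dilation (mean) and pelvic floor symptoms (mean difference from baseline) will be compared as a continuous variables", by Student's t test.
- The next sentence reads: "Binary logistic regression will be used to assess the influence of various patient factors on the patient reported ease of dilation". It extends the method to pelvic floor symptoms and adds that "results will be reported as odds ratios with 95% confidence intervals".
- The same section says that every result with p below 0.05 "will be deemed statistically significant".

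The factors for this model are not named. Data Collection lists variables to be recorded (age, BMI, hormone therapy, orchiectomy, comorbidities, chronic pain, complications, later therapy use) but does not say which enter the regression.

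**The concern.** Two adjacent sentences put the same outcomes on different scales. A binary logistic model has no outcome to fit until someone decides which scores count as easy dilation and which symptom changes count as improvement, and the plan leaves that decision open. Three things follow.

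1. The analysis cannot be reproduced from the plan.
2. Whatever cut is chosen, differences between patients on the same side of it are lost, in a trial that is already small.
3. If the cut and the factors are chosen after the data are seen, the p < 0.05 rule no longer has its nominal error rate, yet the results would be reported as significant or not with no exploratory label.

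Only this supporting analysis is at stake. It answers none of the listed aims, and the treatment comparison does not depend on it.

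**Working it through.** **Inputs from the plan.** Ease of dilation is scored 0-10. There are 17 evaluable and 20 recruited patients per arm, so n = 34 to 40. Significance is p < 0.05, taken here as two-sided. The plan gives no score distribution, factor prevalence or factor effect, so those below are assumptions.

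**The plan's own figure.** It states that "17 subjects in each arm were needed to detect a difference of 2 (+/-1) points between the two groups" at 80% power. The normal approximation is n per arm = 2(1.960 + 0.842)² / (difference/SD)².

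- Difference 2, SD 2: 2 × 7.85 / 1 = 15.7, so 16. The exact t calculation gives 16.7, so 17, which matches. Power at 17 per arm is 81%.
- Difference 2, SD 1: 2 × 7.85 / 4 = 3.9, so 4 (exact t: 6), which does not match.

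An SD of about 2 is therefore used below. The unlabelled ±1 is a separate matter.

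**Information kept by a cut.** For a normal outcome cut at quantile q with standard normal cut-point c, large-sample efficiency relative to linear regression is φ(c)² / [q(1 − q)].

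| Cut | Efficiency | 34 patients count as | 40 count as |
|---|---|---|---|
| Median | 0.159/0.25 = 0.637 (= 2/π) | 22 | 25 |
| 75th percentile | 0.101/0.1875 = 0.539 | 18 | 22 |
| 80th percentile | 0.0784/0.16 = 0.490 | 17 | 20 |

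**Power at the actual size.** One continuous factor has correlation ρ with a normal outcome. Linear regression is compared with a likelihood-ratio logistic test after a median split (10,000 runs).

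| n | ρ | Linear | Logistic |
|---|---|---|---|
| 34 | 0.3 | 42% | 32% |
| 34 | 0.4 | 66% | 48% |
| 34 | 0.5 | 87% | 70% |
| 40 | 0.3 | 48% | 34% |
| 40 | 0.4 | 75% | 56% |
| 40 | 0.5 | 92% | 77% |

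With treatment arm in both models and an arm effect of 1 SD (2 points, SD 2):

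- n = 34: 38% against 28% at ρ = 0.3 (a separate simulation), 65% against 45% at 0.4, and 86% against 64% at 0.5.
- n = 40: 73% against 51% at 0.4, and 92% against 72% at 0.5.

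In the arm-adjusted runs with no factor effect, the logistic test rejects 6.3-7.2% of the time and the linear test 4.7-5.3%. The comparison therefore slightly favours logistic.

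**A fixed cut named in advance.** Integer 0-10 score, mean 5, SD 2, n = 34. Linear power is about 65% at ρ = 0.4 and 85% at 0.5. Logistic power is 45% and 64-65% with a cut at 5 or 6, 39% and 58% at 7, and 30% and 44% at 8.

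**A two-level factor.** With a 2-point shift on the same score, n = 34 and arm in the model, power is 58% against 42% at 20% prevalence and 79% against 61% at 50%. In a simpler model (normal outcome, factor split 50/50, 1-SD shift, no arm term) with an 80/20 cut, an empty cell and hence no finite odds ratio occurs in about 21% of samples at n = 34 and 15% at n = 40.

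**A cut chosen after the fact.** For a factor with no effect (integer score, mean 5, SD 2), taking the best of four cuts (4, 5, 6 or 7) gives a false-positive rate of about 18% at n = 34 and 17% at n = 40, against about 5% for linear regression. This shows what the open choice allows, not what anyone intends.

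**The case against.** The strongest reply is that the defect is only an undefined cut. A justified cut stated in advance would make the analysis runnable, and a team may prefer an odds ratio for easy dilation and accept the loss of power. This is correct as far as it goes. The case for linear regression over a stated cut is one of efficiency, and of keeping the scale of the plan's own t test.

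Linear regression is also not best everywhere. With scores piled near the ceiling (mean 8.5), a 20%-prevalence factor and n = 34, its power is 40%, against 44% for binary and 57% for ordinal logistic regression. The ordinal figure is somewhat flattered, because in a similar setting that test rejects about 7.5% of the time under the null. The plan gives no score distribution that would settle which case applies.

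Correlations of 0.4 to 0.5 are large. At 0.3 both methods are weak. The integer-score simulations cover only the 0-10 scale, not the questionnaire change scores.

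The aim of describing the incidence of dysfunction might suggest a binary outcome. But that aim is preoperative, states no cut and does not cover ease of dilation.

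These points limit the size of the loss and the strength of the preference. None of them supplies the missing binary outcome.

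**Conclusion.** The concern holds. The plan names a method that needs a two-category outcome, applies it to two outcomes it defines and otherwise analyses as continuous, and gives no cut. That conclusion rests on the text alone.

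The cost of a cut rests on assumed normal or rounded-normal scores, SD 2 and assumed factor effects. In large samples it is 36% of the information at the median and more at uneven cuts. In power at n = 34 to 40 with arm in the model, it is about 20 percentage points at correlations of 0.4 to 0.5, and about 10 points at 0.3 (n = 34). The advantage of linear regression can vanish with a marked ceiling and an uncommon factor.

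The primary t test, the sample size and the treatment conclusion are unaffected. This should be corrected, but it does not threaten the trial.

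**What to change.** Replace the logistic regression sentence in POWER ANALYSIS & STATISTICS with wording such as:

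> The influence of patient factors will be explored by linear regression of the 12-week VAS score, and of the change from baseline in each symptom score, on treatment arm plus a small number of baseline factors named before the data are seen. Results will be reported as mean differences with 95% confidence intervals and labelled exploratory.

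- Choose the factors from the baseline items already listed under Data Collection, and keep them few for 34 to 40 patients. Complications and later therapy use arise after randomisation and are not baseline factors.
- For the symptom scores, include the baseline score in the model as well.
- If odds ratios are wanted, or a ceiling is expected, name ordinal logistic regression in advance instead, noting that its likelihood-ratio test is slightly liberal at n = 34 (about 5.5-8% under the null). Do not switch method on observed skewness.
- If robust standard errors are used, specify HC3.
- If a binary outcome is kept, state and justify the cut before the data are seen, and accept the loss of power shown above.

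The cost is SAP wording only, with the same data and no added patients. Results become mean differences rather than binary odds ratios, and fewer factors are examined.

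### Every p<0.05 is to be called significant although only one comparison was sized; limit the significance claim to that comparison, or fix a testing order

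*Combined protocol and SAP*

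**What the plan says.** The rule stands near the end of Power Analysis & Statistics: all results with p below 0.05 "will be deemed statistically significant". It has no qualifier.

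The same section sizes one comparison, ease of dilation between No Postoperative PFPT and Postoperative PFPT: "We determined that 17 subjects in each arm were needed" "to detect a difference of 2 (+/-1) points between the two groups", "with 80% power and a significance level of 0.05". It "will plan to recruit 20 subjects to each arm, for a total of 40 subjects".

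Other analyses fall under the rule:

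- **Symptom scales.** Pelvic floor symptoms are compared between arms by t test, as change from baseline. Study Questionnaires & Exams lists three instruments given both before surgery and at 12 weeks: CRAD-8, UDI-6 and PFIQ-7.
- **Sub-arm contrast.** Postoperative PFPT alone is compared with pre- and postoperative PFPT. Power Analysis & Statistics treats this as a subgroup analysis. In Study Methods, the secondary aims repeat the line "Primary Outcome: Patient reported ease of dilation at 12 weeks (VAS 0-10" that also stands under the primary aim.
- **Regressions.** "Binary logistic regression will be used to assess the influence of various patient factors on the patient reported ease of dilation", and on pelvic floor symptoms as well. The factors are neither named nor counted.
- **Per-protocol repeat.** This is planned as a sensitivity analysis.

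No section gives a multiplicity adjustment, a testing order or a statement that any analysis is exploratory.

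**The concern.** This is more than silence about multiplicity. The plan adopts a rule that attaches the label significant to any result below 0.05, whether or not the trial was designed to test it. With 40 patients, and fewer in the sub-arm contrast, a symptom-scale, sub-arm or patient-factor result could be reported as significant when it is no more than chance would often produce. The text gives readers no statistical basis for ranking such a result below the sized comparison. The repeated primary-outcome label under the secondary aims makes this easier for the sub-arm contrast.

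**Working it through.** **1. The plan's own figure.** Inputs from Power Analysis & Statistics: 17 per arm, difference 2, power 80%, alpha 0.05. Sidedness is not stated; two-sided is assumed. The normal approximation is n = 2(1.960 + 0.842)² × (SD/difference)².

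- SD 1 (reading the ±1 as an SD): 2 × 7.85 × 0.25 = 3.9, so 4 per arm (6 by exact t test). This does not give 17.
- Difference equal to 1 SD: 2 × 7.85 = 15.7, so 16 per arm. The exact t test gives 17, with power 80.7%.

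The 17 therefore fits a two-sided t test for a 1 SD difference. It belongs to one comparison at an undivided alpha of 0.05.

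**2. Number of t tests (inferred).** Outcomes: ease of dilation plus three scales with a baseline = 4. Contrasts: No PFPT against pooled PFPT, and sub-arm against sub-arm = 2. This gives 4 × 2 = 8. No single section lists all eight.

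**3. Chance of at least one false significant result, all nulls true, independent tests:** 1 − 0.95^m.

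| Tests | m | Chance |
|---|---|---|
| Sized comparison alone | 1 | 5.0% |
| Four outcomes, main contrast | 4 | 18.5% |
| Four outcomes, both contrasts | 8 | 33.7% |

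**4. Allowing for correlation.** Outcomes in the same patients are correlated, but the two contrasts are essentially not. With equal sub-arms A and B, the covariance of (none − (A + B)/2) with (A − B) is −½Var(A) + ½Var(B) = 0. Correlation therefore belongs within each contrast only. Simulation (40 patients as 20/10/10, 10,000 runs per setting) gives:

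| Correlation between outcomes | 4 tests, one contrast | 8 tests, both contrasts |
|---|---|---|
| 0.3 | about 17.5% | about 32% |
| 0.5 | about 16% | about 29% |
| 0.7 | about 13% | about 25% |

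Check at 0.5: 1 − (1 − 0.16)² = 29.4%.

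**5. Adding the regressions (illustration only).** The number of factors is not in the plan. The Data Collection list has six patient-factor headings before complications: age, BMI, hormone therapy, orchiectomy, comorbidity and chronic pain. The simulations split each regression outcome at its median, which is also an assumption.

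- Six factors on two regression outcomes: 8 + 12 = 20 tests, 1 − 0.95^20 = 64.2% if independent; about 56 to 65% at correlations of 0.7 to 0.3.
- Three factors on two outcomes: 8 + 6 = 14 tests, 51.2% if independent; about 43% at correlation 0.7.

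**6. The sub-arm contrast.** The allocation ratio within the PFPT arm is not stated. If it is 1:1, there are about 10 against 10. Power for a 1 SD difference is then 56%. The smallest observed difference that reaches p<0.05 is 2.101 × √(2/10) = 0.94 SD, so a significant result there will tend to overstate the effect.

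**7. After the change.** One test at 0.05 has a 5% chance of a false claim, with 17 per arm and 80.7% power unchanged. By comparison, Bonferroni over eight tests would cut power at 17 per arm to 50.4% and need 28 per arm.

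**The case against.** The strongest reply is that the plan does have a hierarchy: one primary aim, one sized comparison, a sub-arm comparison placed under secondary aims and described as a subgroup analysis, and a per-protocol analysis described as a sensitivity analysis. The regressions are already to be reported as odds ratios with 95% confidence intervals. The primary test is at 0.05 whatever happens to the rest, so the primary conclusion is unaffected. All of this stands. It does not remove the concern, because naming a primary outcome limits false claims only if other results are not declared significant by the same rule.

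Several stronger readings are tempting, and the documents do not support them:

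- **At least one false claim is more likely than not.** The t tests alone give about one in four to one in three. Passing 50% requires an assumed number of regression tests.
- **Sixteen tests and a 56% risk.** That count adds PGI-I, pain with dilation, dilator size and vaginal length. These are collected, but the statistics section plans no between-group test for them.
- **Forty-eight regression tests with 2.4 expected false positives.** That treats a data-collection list as a covariate list, splits its headings into 12 single items and tests each against four outcomes. None of this is specified.
- **Two competing primary hypotheses.** The second primary-outcome line is nested under the secondary aims. It is a confusing label, not a second sized hypothesis.

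It is also fair to say that barring all secondary significance claims is not the only sound remedy.

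**Conclusion.** The concern holds in a limited form. The stated rule permits significance claims from analyses that were neither sized nor protected. For the eight t tests that can reasonably be inferred, the risk of at least one false claim is about 34% under independence, or about 25 to 32% with within-contrast correlation of 0.7 to 0.3, against 5% for the sized test. The regressions raise it further; 64% for 20 independent tests is an example, not an estimate.

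These figures rest on all nulls being true (real effects leave fewer claims that can be false), on the t test being used for the sub-arm contrast as well as the main one, and, in the simulations, on a 1:1 sub-arm split. The error control of the primary comparison is not in question. The point should be corrected before analysis, but it does not threaten the main result.

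**What to change.** Replace the significance sentence in Power Analysis & Statistics with wording such as: *Only the primary comparison (ease of dilation at 12 weeks, No PFPT versus pooled Postoperative PFPT, intention to treat) is tested for significance, at two-sided 0.05. The symptom scales, the sub-arm contrast and the regressions are exploratory, and the per-protocol repeat is supportive; all are reported as estimates with 95% confidence intervals and without claims of significance.*

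An equally valid alternative, if the sponsor wants formal claims on symptoms, is to name the scales in a fixed order after the primary test, each tested at 0.05 only if all before it succeed. The sub-arm contrast and regressions would stay exploratory.

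In Study Methods, relabel the outcome under the secondary aims so that only one contrast carries the word primary.

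The cost is one sentence and one label. Secondary results lose an unqualified significance claim. The primary test's alpha, power and sample size stay as they are.
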